### **Pregnancy testing**

Medically supervised pregnancy tests with a minimum sensitivity of 50 mIU/mL must be performed for females of childbearing potential, including females of childbearing potential who commit to complete abstinence, as outlined below.

### **Before starting lenalidomide**

#### ***Female Patients:***

FCBP must have negative pregnancy test 24 hours prior to prescribing lenalidomide. The patient may not receive lenalidomide until the Investigator has verified that the results of these pregnancy tests are negative.

#### ***Male Patients:***

Must agree to practice complete abstinence or agree to use a condom during sexual contact with pregnant females or females of childbearing potential throughout the entire duration of lenalidomide treatment, during dose interruptions and for at least 28 days following lenalidomide discontinuation, even if he has undergone a successful vasectomy.

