### **3. PATIENT SELECTION**

#### **3.1 Inclusion Criteria**

- 3.1.1. Patients must have a Confirmed diagnosis of non-M3 AML. Antecedent MDS is acceptable.
- 3.1.2. Post autologous Stem Cell Transplant Bone marrow biopsy core that is consistent with morphologic remission.
- 3.1.3. Age between 60 and 80years old.
- 3.1.4. Must have received induction and consolidation chemotherapy, and autologous stem cell transplant for AML.
- 3.1.5. Life expectancy of greater than 12 months.
- 3.1.6. Karnofsky Performance Status 70 or greater (see Appendix A)
- 3.1.7. Patients must have normal organ and marrow function as defined below:
  - Leukocytes  $\geq 2,000/\text{mCL}$
  - Absolute neutrophil count  $\geq 1,000/\text{mCL}$
  - Platelets  $\geq 75,000/\text{mCL}$
  - Total bilirubin  $\leq 4 \times$  institutional upper limit of normal unless 2nd to Gilbert's disease
  - AST(SGOT) and ALT(SGPT)  $\leq 4 \times$  institutional upper limit of normal
  - Creatinine  $< 1.5 \times$  institutional upper limit of normal OR creatinine clearance  $\geq 30 \text{ mL}/\text{min}/1.73 \text{ m}^2$  for patients with creatinine levels above institutional normal.
- 3.1.8 Able to take aspirin, or warfarin, or low molecular weight heparin as prophylactic anticoagulation.
- 3.1.9. Ability to understand and the willingness to sign a written informed consent document.
- 3.1.10 Must be registered into the mandatory RevAssist® program and be willing and able to comply with the requirement of RevAssist®.

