#### **3.2 Exclusion Criteria**

- 3.2.1. Patient received chemotherapy or radiotherapy within 2 weeks prior to entering the study or has not recovered from adverse events due to agents administered more than 4 weeks earlier.
- 3.2.2 Patient received another investigational agent after post autologous stem cell transplant.
- 3.2.3 Patient who will be receiving another investigational product during the study.

- 3.2.4 Patient who is growth factor or transfusion dependent.
- 3.2.5 Patient has CNS leukemia.
- 3.2.6 History of allergic reactions attributed to thalidomide or lenalidomide.
- 3.2.7 History of erythema nodosum, characterized by a desquamating rash while taking thalidomide or similar drugs.
- 3.2.8 Prior history of metastatic malignancy.
- 3.2.9 Uncontrolled illness including, but not limited to ongoing or active infection, unstable angina pectoris, cardiac arrhythmia, or psychiatric illness/social situations that would limit compliance with study requirements. Patients must not have suffered recent (< 6 months) myocardial infarction, unstable angina, uncontrolled hypertension, or difficult to control cardiac arrhythmias.
- 3.2.10 Evidence of uncontrolled Congestive Heart Failure (CHF).
- 3.2.11 Active Hepatitis B as defined by Hepatitis B surface antigen positivity, unless able to start dual anti-HepB therapy, or already on dual anti-HepB therapy
- 3.2.12 Patients who are positive for Hepatitis B core antibody, but negative for the hepatitis B surface antigen, should be on lamivudine 100 mg daily until at least 3 months post-transplant
- 3.2.13 Patient is positive for HIV or HTLV-1.
- 3.2.14 Women of childbearing potential (defined as a sexually mature woman who has not undergone a hysterectomy or who has had menses at any time in the preceding 24 consecutive months).
- 3.2.15 Men who did not agree not to father a child and who refused to use a latex condom during any sexual contact with women of childbearing potential while taking lenalidomide and for 4 weeks after therapy is stopped, even if they have undergone a successful vasectomy.

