3.1.6. Karnofsky Performance Status 70 or greater (see Appendix A)		
3.1.7. Patients have normal organ and marrow function as defined below: - Leukocytes $\geq 2,000/\text{mL}$ - Absolute neutrophil count $\geq 1,000/\text{mL}$ - Platelets $\geq 75,000/\text{mL}$ - Total bilirubin $\leq 4 \times$ institutional upper limit of normal unless 2nd to Gilbert's disease - AST(SGOT) and ALT(SGPT) $\leq 4 \times$ institutional upper limit of normal - Creatinine $< 1.5 \times$ institutional upper limit of normal OR creatinine clearance $\geq 30 \text{ mL/min/1.73 m}^2$ for patients with creatinine levels above institutional normal.		
3.1.8 Able to take aspirin, or warfarin, or low molecular weight heparin as prophylactic anticoagulation.		
3.1.9. Ability to understand and the willingness to sign a written informed consent document.		
3.1.10 Patient will be registered into the mandatory RevAssist® program and be willing and able to comply with the requirement of RevAssist®.		

Exclusion Criteria:	YES	NO
The answers to the following questions must be NO in order for the patient to be eligible.		
3.2.1. Patient received chemotherapy or radiotherapy within 2 weeks prior to entering the study or has not recovered from adverse events due to agents administered more than 4 weeks earlier.		
3.2.2 Patient received another investigational agent after post autologous stem cell transplant.		
3.2.3 Patient will be receiving another investigational product during the study.		
3.2.4 Patient who is growth factor or transfusion dependent.		
3.2.5 Patient has CNS leukemia.		
3.2.6 Patient has a history of allergic reactions attributed to thalidomide or lenalidomide.		
3.2.7 Patient has a history of erythema nodosum, characterized by a desquamating rash while taking thalidomide or similar drugs.		
3.2.8 History of metastatic malignancy.		
3.2.9 Presence of uncontrolled illness including, but not limited to ongoing or active infection, unstable angina pectoris, cardiac arrhythmia, or psychiatric illness/social situations that would limit compliance with study requirements. Patients must not have suffered recent (< 6 months) myocardial infarction, unstable angina, uncontrolled hypertension, or difficult to control cardiac arrhythmias.		
3.2.10 Evidence of uncontrolled Congestive Heart Failure (CHF).		

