3.2.11 Active Hepatitis B as defined by Hepatitis B surface antigen positivity, unless able to start dual anti-HepB therapy, or already on dual anti-HepB therapy		
3.2.12 Patient is positive for Hepatitis B core antibody, but negative for the hepatitis B surface antigen, and is on lamivudine 100 mg daily until at least 3 months post-transplant		
3.2.13 Patient is positive for HIV or HTLV-1.		
3.2.14 Patient is woman of childbearing potential (defined as a sexually mature woman who has not undergone a hysterectomy or who has had menses at any time in the preceding 24 consecutive months).		
3.2.15 Patient is a man who agreed not to father a child and agreed to use a latex condom during any sexual contact with women of childbearing potential while taking lenalidomide and for 4 weeks after therapy is stopped, even if they have undergone a successful vasectomy.		

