#### ***The investigator must ensure that:***

- Females of childbearing potential comply with the conditions for pregnancy risk minimization, including confirmation that she has an adequate level of understanding.
- Females NOT of childbearing potential acknowledge that she understands the hazards and necessary precautions associated with the use of lenalidomide.
- Male patients taking lenalidomide acknowledge that he understands that traces of

lenalidomide have been found in semen, that he understands the potential teratogenic risk if engaged in sexual activity with a female of childbearing potential or pregnant female, and that he understands the need for the use of a condom even if he has had a vasectomy, if engaged in sexual activity with a female of childbearing potential or pregnant female.

- Subject is continuing to use two reliable methods of birth control at each visit during the time that birth control is required.
- If pregnancy or a positive pregnancy test does occur in a study patient, lenalidomide must be immediately discontinued.
- Pregnancy testing and counseling must be performed if a patient misses her period or if her pregnancy test or her menstrual bleeding is abnormal. Lenalidomide treatment must be temporarily discontinued during this evaluation.
- Females must agree to abstain from breastfeeding during study participation and for at least 28 days after lenalidomide discontinuation.
- male subjects must practice complete abstinence or use a condom during sexual contact with pregnant females or females of childbearing potential throughout the entire duration of lenalidomide treatment, during dose interruptions and for at least 28 days following lenalidomide discontinuation, even if he has undergone a successful vasectomy.
- If pregnancy or a positive pregnancy test does occur in the partner of a male study patient during study participation, the investigator must be notified immediately.
- Male patients are instructed not to donate semen or sperm during therapy or for at least 28 days following discontinuation of lenalidomide.

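### Read literally, exclusion 3.2.15 and its Form 1 item both pass a sexually active man who agrees not to father a child but refuses condoms, although Appendix F would not let him start lenalidomide

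*Combined protocol and SAP*

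**What the plan says.** Four places in the protocol bear on what a male patient must undertake.

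- **Section 3.2, exclusion 3.2.15** excludes "Men who did not agree not to father a child and who refused to use a latex condom during any sexual contact"; the partners meant are women who could become pregnant. The condition runs through treatment and "for 4 weeks after therapy is stopped, even if they have undergone a successful vasectomy".
- **Appendix B, Form 1, exclusion item 3.2.15** turns the sentence round: "Patient is a man who agreed not to father a child and agreed to use a latex condom during any sexual contact". The rule at the head of that part of the form is "The answers to the following questions must be NO in order for the patient to be eligible".
- **Appendix F, Male Patients**, under the heading on what must happen before lenalidomide is started: "Must agree to practice complete abstinence or agree to use a condom during sexual contact with pregnant females or females of childbearing potential". This covers treatment and dose interruptions, and continues "for at least 28 days following lenalidomide discontinuation, even if he has undergone a successful vasectomy". The list of investigator duties that follows repeats the requirement and adds that the man must acknowledge that "he understands the need for the use of a condom even if he has had a vasectomy", because traces of the drug have been found in semen.
- **Section 3.1, inclusion 3.1.10** requires every patient to be registered in the RevAssist "program and be willing and able to comply with the requirement of RevAssist".

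**The concern.** A vasectomised man can easily promise not to father a child and see no reason to use condoms. Section 3.2.15 closes with a clause about vasectomy, so its authors had this man in mind. As worded, however, his promise on the first point is enough to keep him clear of the exclusion. Appendix F offers no such exchange: an undertaking not to father a child does not stand in for abstinence or a condom.

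The eligibility section and the fetal-risk appendix therefore classify the same man differently. Sections 4.1 and 4.2 have the Study Coordinator verify eligibility from Form 1 before registration, and treatment is expected within 96 hours after it. A mismatch found only at prescribing leaves a registered patient who should not be treated. A mismatch that is missed leaves a safeguard resting on one appendix. Appendix F says that human teratogenicity cannot be ruled out, so the potential harm is severe even if the event is rare.

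**Working it through.** No statistical quantity is involved, and the plan gives no figure to reproduce. The check is a truth table on two yes/no undertakings.

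Let A mean that the man agreed not to father a child, and C that he agreed to use condoms. Consider a sexually active man, that is, one who does not commit to complete abstinence and whose partner is within the scope of the rule.

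The rules, as literally worded:

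- Section 3.2.15 excludes if (not A) and (not C).
- Form 1 item 3.2.15 is answered YES if A and C. NO is needed for eligibility, so the form excludes if A and C.
- Appendix F is met if C holds. Complete abstinence also meets it, but is set aside here by assumption. A plays no part.

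| A: agrees not to father | C: agrees to condom | Section 3.2.15 | Form 1 item | Appendix F |
|---|---|---|---|---|
| yes | yes | not excluded | excluded | met |
| **yes** | **no** | **not excluded** | **not excluded** | **not met** |
| no | yes | not excluded | not excluded | met |
| no | no | excluded | not excluded | not met |

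Reading across the rows:

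1. Section 3.2.15 excludes 1 of the 4 combinations; Appendix F is failed in 2 of the 4. They disagree in one row, the second.
2. In that row Form 1 does not repair the gap. The man has not agreed to both undertakings, so the truthful answer is NO and he passes.
3. Form 1 disagrees with Appendix F in 3 of the 4 rows (first, second and fourth). The first and fourth come from the reversed YES/NO sense of the form item. That is a related fault, separate from the connective in 3.2.15.
4. The durations do not conflict: 4 weeks × 7 days = 28 days, and both texts disallow a vasectomy exception.
5. The content of the undertakings also differs. Section 3.2.15 asks for a promise not to father a child and specifies latex; Appendix F asks for neither. Appendix F names abstinence, pregnant partners and dose interruptions; 3.2.15 names none of them.

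**The case against.** **The intent is clear enough.** The repeated *who* in 3.2.15 allows a reading in which two separate groups of men are excluded. The vasectomy clause makes little sense if a promise not to father a child cures a refusal of condoms, and Form 1 puts the two undertakings together as if both were wanted. This is persuasive on intent: it is a slip in a connective, not a deliberate design. It does not remove the point, because eligibility is verified against written criteria, and one that must be read against its grammar can be applied differently by different sites.

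**He would still not be treated.** A reader might infer that this man is simply eligible and would receive the drug. The documents do not support that. Appendix F sets a condition before dosing and gives the investigator a duty to ensure that male subjects comply, so exposure would require Appendix F to be overlooked too. Inclusion 3.1.10 may stop him as well, although the documents do not say what RevAssist asks of men, so that safeguard cannot be confirmed from them.

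**Other stronger readings fail.**

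- It is tempting to say that, with women of childbearing potential excluded by 3.2.14, male patients' partners are the only remaining route of fetal exposure. The protocol itself addresses others: handling of capsules by women of childbearing potential (Section 2.5), and sharing of drug and blood donation (Appendix F).
- It is tempting to treat the silence of 3.2.15 on abstinence as a second conflict. A completely abstinent man who agrees not to father a child is not excluded by 3.2.15 and meets Appendix F, so no difference in classification is shown for him.
- Correcting Form 1 need not carry the gap forward. Reversing the required answer on its existing wording would exclude any man who has not agreed to both undertakings, including this one. The gap would carry over only if the text of 3.2.15 were copied in.

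**Conclusion.** The inconsistency is real and limited. On the literal wording, a sexually active man who agrees not to father a child but refuses condoms is caught neither by 3.2.15 nor by its Form 1 item, and could be registered although Appendix F requires an undertaking he has not given before he starts lenalidomide.

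The conclusion rests on three assumptions: that *and* in 3.2.15 is read in its ordinary sense, that Form 1 is answered truthfully as worded, and that the man is not committed to complete abstinence. It does not establish that such a man would be dosed.

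The documents do not say how many men are affected. In a population aged 60 to 80 the number is probably small. No endpoint, dose decision or analysis depends on it. The case for correcting it is the severity of the possible harm set against a very small drafting cost.

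**What to change.** Reconcile Section 3.2.15, Form 1 item 3.2.15 and Appendix F so that all three state the same male undertaking. The sponsor should choose its content, deciding explicitly on each term that now appears in only one place: not fathering a child, latex, complete abstinence, pregnant partners and dose interruptions. This review takes no position on which of these belong.

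Whatever is chosen, the wording of 3.2.15 and the required YES/NO answer on Form 1 should be such that failing the undertaking excludes. Replacing *and* with *or* in 3.2.15 would close the case described, but would leave the form reversed and the terms unaligned.

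The cost is one sentence in Section 3.2 and one line on Form 1, plus matching words in Appendix F if the sponsor's choice differs from what stands there. The effect on accrual should be negligible if, as is likely, few men are concerned.

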#### ***The investigator must ensure that:***

- Females of childbearing potential comply with the conditions for pregnancy risk minimization, including confirmation that she has an adequate level of understanding.
- Females NOT of childbearing potential acknowledge that she understands the hazards and necessary precautions associated with the use of lenalidomide.
- Male patients taking lenalidomide acknowledge that he understands that traces of

lenalidomide have been found in semen, that he understands the potential teratogenic risk if engaged in sexual activity with a female of childbearing potential or pregnant female, and that he understands the need for the use of a condom even if he has had a vasectomy, if engaged in sexual activity with a female of childbearing potential or pregnant female.

- Subject is continuing to use two reliable methods of birth control at each visit during the time that birth control is required.
- If pregnancy or a positive pregnancy test does occur in a study patient, lenalidomide must be immediately discontinued.
- Pregnancy testing and counseling must be performed if a patient misses her period or if her pregnancy test or her menstrual bleeding is abnormal. Lenalidomide treatment must be temporarily discontinued during this evaluation.
- Females must agree to abstain from breastfeeding during study participation and for at least 28 days after lenalidomide discontinuation.
- male subjects must practice complete abstinence or use a condom during sexual contact with pregnant females or females of childbearing potential throughout the entire duration of lenalidomide treatment, during dose interruptions and for at least 28 days following lenalidomide discontinuation, even if he has undergone a successful vasectomy.
- If pregnancy or a positive pregnancy test does occur in the partner of a male study patient during study participation, the investigator must be notified immediately.
- Male patients are instructed not to donate semen or sperm during therapy or for at least 28 days following discontinuation of lenalidomide.

#### **Additional precautions**

- Subjects should be instructed never to give lenalidomide to another person.
- Subjects should not donate blood during therapy and for at least 28 days following discontinuation of lenalidomide.
- Only enough lenalidomide for one cycle of therapy may be prescribed with each cycle of therapy.
- Any unused lenalidomide must be returned as instructed through RevAssist program.

## Appendix G – Drug insert and Full Prescribing Information

Most recent drug insert; highlights and full prescribing information for lenalidomide are available online at:

<http://www.revlimid.com/docs/Revlimid-Full-PI.pdf>

**Appendix H: FDA MEDWATCH 3500A Form:**

FDA MedWatch 3500A Form is available online at:

<http://www.fda.gov/downloads/AboutFDA/CentersOffices/CDER/ucm103114.pdf>

## Appendix I : NCI CTCAE Version 4.0

Toxicity will be scored using NCI CTC Version 4.0 for toxicity and adverse event reporting. A copy of the NCI CTC Version 4.0 can be downloaded from the CTEP homepage: (<http://ctep.info.nih.gov>).

All appropriate treatment areas have access to a copy of the CTC Version 4.0

